10.6.3 Secondary outcome analysis

The electronic health record system audit logs will be used to assess whether each structured data item suggested by MiADE is accepted by the clinician. Descriptive statistics will be calculated for this proportion among subgroups such as inpatients and outpatients, and the distribution among clinicians in the study will be calculated.

The distribution of computing times per consultation note will be calculated and summarised (mean, standard deviation, median and interquartile range).

Descriptive statistics will be calculated for each of the survey questions.

A full descriptive analysis of qualitative data will be conducted to meet study objectives. Interview transcripts and observation notes will be analysed using thematic coding mapped to the theoretical domains framework to understand the cognitive, affective, social, environmental, organisational and professional influences on behaviours relating to the use of MiADE. A researcher will code emerging themes drawing on the theoretical frameworks that underpin the interview schedule and topic

guide. An iterative approach using constant comparison will be employed in the development of coding frames and coding of data. A second researcher will read all the transcripts and code a sample to ensure reliability. Emerging themes from patient interviews will be discussed at team meetings and shared with our patient representatives to confirm that interpretations made by researchers stay close to the direct experience of patients

Interview findings from patient and clinician interviews will be transcribed, coded and findings aggregated into themes.

10.6.4 Sensitivity and other planned analyses

Subgroup analyses for the completeness of structured data recording will be carried out by clinical specialty and seniority of doctor. Correlations between clinician characteristics in the pre-MiADE survey and the difference in mean number of structured entries with MiADE for outpatients will be explored.

Secondary analyses will be carried out to compare recording of structured data between the following time periods:

- 1. Before consent versus before MiADE. This will assess the Hawthorne effect, i.e. if there is any change in clinician behaviour once they know they are in the study. This will provide useful information for future interventions to improve structured data recording.
- 2. Before consent versus after MiADE. This will assess the overall effect of the complex intervention (i.e. the whole programme of training, institutional buy-in for quality improvement, as well as the tool to assist clinicians).

There are no relevant stopping criteria.

11.ASSESSMENT AND MANAGEMENT OF RISK

The table below summarises the risks and mitigations of all interventions above standard care that are being performed:

Intervention	Potential risk	Risk Management
Entering clinical data using MiADE	MiADE may return an inaccurate suggestion (possible)	The clinician has to actively review a suggestion in order to add it to the record, so there is minimal risk that an incorrect entry will be added to the patient record.
Entering clinical data using MiADE	Clinicians may not use the system appropriately (possible)	Training will be provided and access will be limited to clinicians who have completed training.
Entering clinical data	The MiADE system may malfunction	The MiADE system is separate from Epic and works in the

using MiADE	(unlikely)	background, so users can continue with their Epic work regardless of the activity of MiADE. If Epic does not receive a reply from MiADE in a reasonable time it will timeout the request. If the MiADE system is completely down, clinicians will be able to use Epic just as before, without MiADE.
Entering clinical data using MiADE	The MiADE system may perform poorly and be a hindrance to clinicians (unlikely)	Clinicians can choose to ignore the recommendations from MiADE or switch the system off at any time.

12.RECORDING AND REPORTING OF ADVERSE EVENTS

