Trial design and methods:	The trial consists of two non-randomised intervention substudies with before and after comparison (outpatient and inpatient), with embedded qualitative substudies involving clinician interviews and (in the outpatient setting only) observed consultations and patient interviews. Clinicians will be recruited, consented and provided with training to use the MiADE system. The system will be switched on at a particular time point, and clinical records for patients seen before and after the system was switched on will be compared. The primary outcome will be the comparison of the number of diagnoses, medication and allergies entered in a structured way per	

	patient. A rapid ethnography-based approach will be used to observe a subset of patient consultations to find out how clinicians are using the system, and semi-structured interviews will be held with patients and clinicians to understand the effect of social, cultural and behavioural information on human experiences and practices.
Trial duration per participant:	5 months
Key Study milestones	Jul 2023: Clinician recruitment and consent
	Aug 2023: Training of clinicians, surveys and observed consultations without MiADE
	Sep 2023: MiADE switch on
	Oct 2023: Interviews, surveys and observed consultations with MiADE
	Nov 2023: Study end
	Dec 2023 – Jan 2024: Data analysis
Estimated total trial duration:	7 months
Planned trial sites:	Single-site, UCLH
Total number of	Outpatient study:
participants planned:	Clinicians using MiADE: at least 25, target 50
	Patients for analysis of pseudonymised health record: estimated 3000 (assuming 25 clinicians each see 5 new patients per week, and 24 weeks of data are analysed)
	Clinicians for observed consultations and interview: 5
	Patients for observed consultation and interview: at least 20 (10 before MiADE, 10 after MiADE)
	Inpatient study:
	Clinicians using MiADE: at least 25, target 50
	Patients for analysis of pseudonymised health record: estimated 600 (assuming 5 inpatient teams each discharge 5 patients per week, and 24 weeks of data are analysed)
Main inclusion/exclusion criteria:	Electronic health record of patients being seen in clinics under the care of participating clinicians
Statistical methodology	Outpatients: comparison (pre- and post-intervention) of mean

Feasibility study of 'MiADE' point of care natural language processing, EDGE number 157134, IRAS number 322887, Protocol, Version 1.1, DATE 24/07/2023

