4. TRIAL DESIGN

This study consists of two substudies (inpatient and outpatient studies), each of which is a nonrandomised intervention study with before and after comparison. The outpatient study also includes an embedded qualitative substudy for a subset of consultations, with patient and clinician interviews. A subset of clinicians will also be interviewed for the inpatient study. The overall clinician participant flow is illustrated in Figure 2.

[figure not shown]

Figure 2: Study flow diagram showing how clinicians will move through the study

Three time periods will be analysed. The primary comparison will be for recording of structured information in patient records between pre-MiADE and post-MiADE periods once clinicians have been consented into the study, as they will have received training and the comparison will show the change in behaviour that results from the system being available. There is a possibility that structured recording may improve because of the study itself (i.e. a Hawthorne effect), so a prior 8week period will also be studied in order to evaluate this effect. See figure below for the overall trial design and timing of interventions. The overall study timeline is shown in Figure 3.

The MiADE system will be made available according to clinician-level permissions, which can be switched on or off. This will allow clinicians' use of problem lists and other structured data to be compared before and after the system is switched on. There will be a period of at least 4 weeks between clinicians entering the study and having the MiADE system switched on.

[figure not shown]

Figure 3: Study timeline

Training programme

All clinicians in the study will undergo a standardised training package consisting of viewing a video and reading a user guide, with access to help from the research team by email or phone throughout the study. The training will cover:

- The importance of maintaining problem lists with accurately coded information about a patient's diagnoses
- National and local (UCLH) guidance on the use of problem lists
- How to use the MiADE system
- The aims and methods of the study

Clinicians will not be eligible to enter the study and have the MiADE system switched on for their EHR user profile until they have undertaken the training.

Pre-MiADE questionnaire – questions for all clinicians

- What is your seniority (e.g. FY1, Consultant etc.)?
- What is your specialty?

Pre-MiADE questionnaire – outpatient study

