Consultants and specialty doctors who see outpatients will be recruited via institutional communications and networks. Interested clinicians will be consented and receive training on the use of the system, as described below. They will be asked to fill in a survey on their level of experience and comfort with EHR systems. They will have the MiADE system switched on within their EHR user profile so that they have access to it from a particular date. Electronic health records of outpatients in the clinics linked to the clinician will be assessed for 3 time periods: pre-study (before the training session), between the training session and MiADE switch-on, and for 8 weeks after MiADE is switched on. The crude number of entries per patient in the problem list, medication record and allergy record will be calculated for outpatients seen by the clinician during each interval.

Embedded qualitative substudy

For each clinician in the qualitative substudy, a sample of at least 2 outpatient consultations will be observed before the MiADE system is switched on for the clinician, and at least 2 outpatient consultations will be observed after the MiADE system is switched on. For each observed consultation, consent will be sought from the patient prior to the consultation. The researcher will sit in the consultation and observe the overall consultation, as well as timing the overall consultation and how long the clinician spends interacting with the EHR. The researcher will ask questions to the clinician after the consultation, if necessary, in order to clarify any behaviours observed.

Patient interviews

A semi-structured interview will be held with the patient after the consultation either in person (if clinic space is available) or by telephone, to explore the patient's perception and experience of the consultation.

The interview guide will include questions such as:

- How did you feel about the way that the doctor interacted with the computer in your consultation?
- How did this compare with your experience of previous consultations in this hospital or elsewhere?
- Use and usefulness of the UCLH patient portal (MyCare): prompts include
 - Access to medical diagnoses, allergies and medications on the UCLH patient portal
 - Usefulness of the features
 - Completeness and accuracy of the information
- Would you be interested in being invited to future workshops or other activities to help improve electronic health records?

Study 2 (Inpatient study)

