Inpatient clinical teams will be recruited to the study. Within each team, the clinicians (consultants, specialty and foundation doctors who see inpatients) will be recruited, consented and trained. Doctors rotate through clinical teams every few months, so the MiADE system will be switched on for the relevant clinicians at a time point half-way through the four-month rotation, to allow comparison of the completeness of structured recording of diagnoses on the problem list before and after the switch-on. The 'gold standard' of recording of diagnoses will be the ICD-10 coded billing diagnoses which are assigned by the clinical coding team based on a review of the entire medical record after a patient is discharged. Diagnoses will be aggregated by groups of ICD-10 codes similar to a previous UCLH audit [15], and a diagnosis will be considered as included in the problem list if any SNOMED CT concept which maps to an ICD-10 code in the group was recorded on or prior to the patient's discharge date. This flexibility of mapping will be permitted as different professionals may assign different clinical codes to the same condition based on their interpretation and judgement, especially for cases where an exact code does not exist. The proportion of ICD-10 code groups with a problem list entry will be calculated per patient, and aggregated across the patients under the care of the clinical team during the study period.

For a sample of 5 clinicians, semi-structured interviews will be held with the clinicians after they have been using MiADE for at least two weeks, using the same questions as for outpatient doctors except the question on medications, as MiADE for inpatients does not handle medications.

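### The contrast labelled as a Hawthorne effect also contains the problem-list training (and, for inpatients, probably a change of doctors), and the start of the pre-MiADE baseline is stated inconsistently

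*Protocol*

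**What the plan says.** Section 10.6.4 plans two secondary comparisons of time periods. The first is: "Before consent versus before MiADE. This will assess the Hawthorne effect, i.e. if there is any change in clinician behaviour", the change being put down to clinicians knowing that they are in the study. The second, before consent against after MiADE, is said to capture "the whole programme of training, institutional buy-in for quality improvement, as well as the tool to assist clinicians".

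Section 4 (Training programme) requires every clinician to complete a standard package before switch-on. Its first topic is "The importance of maintaining problem lists with accurately coded information"; national and local guidance on problem lists is also covered.

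The start of the pre-MiADE period is described in two ways. Section 4 states: "The primary comparison will be for recording of structured information in patient records between pre-MiADE and post-MiADE periods once clinicians have been consented", and justifies this by saying that clinicians will by then be trained. Section 4, Study 1, lists the first two outpatient periods as "pre-study (before the training session), between the training session and MiADE switch-on".

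The order of consent and training also varies. The Study Summary milestones put recruitment and consent in July 2023, followed by "Aug 2023: Training of clinicians, surveys and observed consultations without MiADE". Section 7.3.2 describes consent and the training video together, and Appendix 1 places both at visit 1.

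For inpatients, Section 4, Study 2, has MiADE switched on "at a time point half-way through the four-month rotation", because doctors move between teams.

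**The concern.** Training on the value and use of problem lists aims directly at the outcome being measured. A change between the pre-consent period and the trained, pre-switch-on period could come from being in the study, from the training, or from both. Section 10.6.4 attributes it all to the first, although its own second contrast treats training as an active component. The section says that this result should inform future efforts to improve structured recording, so a training effect could be carried forward as an observation effect.

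For inpatients there is a further problem. A period that reaches back before the current rotation was partly recorded by other doctors, so a difference is not simply a change in the behaviour of the same clinicians.

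The inconsistent baseline start matters for a different reason. If some weeks fall between consent and training, the same records are primary baseline under one description and pre-study data under the other. The choice could then be made after the data are seen.

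**Working it through.** **The plan's own figures.** The inpatient record count reproduces: 5 teams × 5 patients × 24 weeks = 600. The 549 problems per group for 62% against 70% (Section 10.3) also reproduces: a pooled two-proportion formula gives 550, assuming two-sided 5% significance and 80% power, which the protocol does not state. Neither figure is in dispute. The 70 − 62 = 8 points serve below only as a scale.

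**Step 1: what each contrast contains.** Let *a* be the effect of study awareness, *g* the effect of training, *m* the effect of MiADE, and *u* the share of the pre-MiADE baseline that precedes training. Assume that the effects add and that there is no time trend.

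- Contrast 1 (before consent v pre-MiADE) = *a* + (1 − *u*)*g*
- Primary (pre- v post-MiADE) = *m* + *ug*
- Contrast 2 (before consent v post-MiADE) = *a* + *g* + *m*, the sum of the other two

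Three periods give two independent contrasts for three unknowns, so *a* cannot be recovered. If consent and training coincide (*u* = 0) and true awareness is zero, an assumed training gain of 2, 4 or 8 points appears in contrast 1 as exactly 2, 4 or 8 points.

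**Step 2: the inpatient rotation.** Inputs: a prior period of 8 weeks (Section 4); *L* weeks from consent to switch-on, at least 4 (Section 7.3.2, Appendix 1); switch-on at the midpoint of four months (Section 4, Study 2).

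- Half a rotation = 2 × 365.25/12/7 = 8.7 weeks.
- The prior period starts *L* + 8 weeks before switch-on, so at least 12.
- Prior weeks that precede the rotation = *L* + 8 − 8.7, capped at 8.

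| *L* (weeks) | Prior weeks before the rotation | Share of 8 weeks |
|---|---|---|
| 4 | 3.3 | 41% |
| 6 | 5.3 | 66% |
| 8 | 7.3 | 91% |
| 8.7 (consent at rotation start) | 8.0 | 100% |

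This assumes that the 8-week prior period applies to inpatients. Section 4 introduces the three periods for the whole study, and the Study Summary plans 24 inpatient weeks. If these are three periods of 8 weeks (my reading), the row for *L* = 8 applies.

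**Step 3: the statements on timing side by side.**

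| Place | Period boundary or timing |
|---|---|
| Section 4, design | Pre-MiADE period starts at consent; training presumed received |
| Section 10.6.4 | Earlier period ends at consent |
| Section 4, Study 1 | Boundary is the training session |
| Study Summary milestones | Consent July, training August |
| Section 7.3.2, Appendix 1 | Consent and training together |

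**Step 4: consequence for the primary contrast.** The bias from training is *ug*, in percentage points on the inpatient proportion:

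| Assumed *g* | *u* = 0 | *u* = 25% | *u* = 50% |
|---|---|---|---|
| 2 | 0 | 0.5 | 1 |
| 4 | 0 | 1 | 2 |
| 8 | 0 | 2 | 4 |

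The protocol gives neither *g* nor *u*; both are assumptions.

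**The case against.** The best defence concerns the primary comparison. A reader might infer that it too fails to isolate MiADE, or that its effect is inflated. The documents do not support that. Appendix 1 puts consent and training at one visit, Section 7.3.2 agrees, and Section 4 bars entry and switch-on until training is done. On those texts the two baseline starts coincide, both primary periods follow training, and the bias is zero. The contrary evidence is one pair of calendar-month milestones, which describe study-wide activity and not any clinician's gap. The related worry that fewer than four trained weeks might precede switch-on depends on the same milestone order. Nor does a figure in percentage points carry over to outpatients, whose primary analysis in Section 10.6.2 is a ratio of counts.

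The mid-rotation switch-on also protects the inpatient primary comparison. A baseline of up to 8.7 weeks and 8 weeks afterwards both fit within one rotation. Section 10.6.2 already analyses inpatients by team and admits that clinicians within a team cannot be told apart. It could be added that contrast 2 names training openly and that contrast 1 is only secondary, in a feasibility study.

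All of this stands, and it limits the point. It does not rescue the label on contrast 1: with consent and training at one visit, awareness and training are completely confounded. Nor does team-level analysis turn a comparison across rotations into a change in the same clinicians' behaviour.

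**Conclusion.** The stated interpretation of contrast 1 is wrong on both timelines that the protocol gives, whether training comes with consent or a month later. It estimates study participation plus training. No figure for awareness alone can be drawn from the three periods.

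For inpatients, contrasts 1 and 2 also compare partly different sets of doctors, on the assumption that the general prior period covers them. The share from the previous rotation is bounded by the protocol's own timings at 41% to 100%. How many doctors in a team actually rotate is not stated, so the effect on the estimate cannot be sized.

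The inconsistent baseline start is a real contradiction, but its effect on the primary result is conditional. It is nil if training accompanies consent. It is about 1 to 2 points, against the 8 points used for planning, if training lags enough to leave 25–50% of the baseline untrained and training is worth an assumed 4 points. The sample size is unaffected.

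**What to change.** 1. In Section 10.6.4, rename contrast 1 *study participation plus training* and remove the Hawthorne interpretation. Align the sentence in Section 4 that introduces the prior period for that purpose.
2. State whether the prior period applies to inpatients. If so, describe inpatient contrasts 1 and 2 as team-level comparisons that span a change of doctors.
3. In Sections 4 and 10.6, start the primary baseline at each clinician's logged date of training completion. Inpatient records cannot be split by clinician, so name one date per team, for example when the last participating doctor completed training.
4. Reconcile the order of consent and training across the Study Summary, Section 4 (design and Study 1), Section 7.3.2 and Appendix 1.
5. Leave any weeks between consent and training out of the primary baseline. Use them as an awareness contrast only if such a gap exists; if both happen at one visit, there are no data for it and renaming is the whole remedy.

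The cost is wording and one logged date per clinician. The downside is slightly fewer baseline weeks for clinicians trained after consent and, with a team date, for teams with a late trainee. The dates should be settled before records are extracted.

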12.1 Definitions

Term	Definition		
Adverse Event (AE)	Any untoward medical occurrence in a patient or trial participant, which does not necessarily have a causal relationship with the intervention involved.		
Serious Adverse Event	Any adverse event that:		
(SAE).	• results in death,		
	 is life-threatening*, 		
	 requires hospitalisation or prolongation of existing hospitalisation**, 		
	• results in persistent or significant disability or incapacity, or		
	• consists of a congenital anomaly or birth defect.		
	• Other 'important medical events' may also be considered serious if they jeopardise the participant or require an intervention to prevent one of the above consequences		
* A life- threatening eve	nt, this refers to an event in which the participant was at risk of death at		

* A life- threatening event, this refers to an event in which the participant was at risk of death at the time of the event; it does not refer to an event which hypothetically might have caused death if it were more severe.

** Hospitalisation is defined as an in-patient admission, regardless of length of stay. Hospitalisation for pre-existing conditions, including elective procedures do not constitute an SAE.

